Primary Objective(s)	To assess the safety and feasibility of gastrostomy tube placement using the PUG technique and the CoapTech device. The primary outcome of interest will be number and severity of device-related adverse events. Any adverse events during the immediate procedural and post-procedural period with a score of 3 or greater ("serious") will be considered unsafe. Of that set, any adverse safety events during the immediate procedural and post-procedural period with a "relatedness to intervention" score of 3 or greater ("probably related") will be considered device-related. See Table 3.
----------------------	---

Secondary Objectives	
 1) While acknowledging that the study is underpowered, to perform a preliminary direct comparison of the following between the PUG placement and a retrospective cohort of matched controls who undergo gastrostomy placement using the percutaneous radiologic gastrostomy (PRG) push gastropexy technique. 
 a) Serious complication rate: a composite rate inclusive of inadvertent puncture of important structures, damage to structures requiring surgical repair and development of infectious complications during the immediate post-procedure period. Important structures are defined a priori as liver, larger blood vessels (that require operative repair or result in significant blood loss in the opinion of the operator), small or large bowel, spleen, etc.. b) Serious adverse events, individually described as: 
 i) Misplacement harm ii) Infection (Sepsis, Peritonitis) iii) Tissue / Organ Damage iv) Requirement for Salvage Surgery and which type(s) v) Other 2) To describe the preliminary rate of other complications during the immediate procedural period between the PUG placement and a historical cohort of matched controls who underwent gastrostomy placement using the PRG technique. 
 a) Tube rupture b) Retained foreign body due to procedure 3) To compare the preliminary cost and operational factors during the immediate procedural period and overall hospital stay between the PUG placement and a retrospective cohort of matched controls who undergo gastrostomy placement using the PRG technique, including:
----------------------	---

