The study population will consist of male and female patients (≥ 18 years old) admitted to the participating study site and in whom the primary clinical team has determined that a gastrostomy tube should be placed. The study will focus on patients with a BMI of 20-30 to avoid complications associated with extremes in body habitus.

Inclusion Criteria

Patients eligible for inclusion in this study have to fulfill all of the following criteria:

- Informed consent must be obtained before any study-specific assessment is performed
- Male or female ≥ 18 years of age
- $20 \leq \text{BMI} \leq 30$
- Indication for gastrostomy tube placement determined to be present by the primary clinical care team
- Patient determined to be an appropriate candidate for gastrostomy by the study team
- Women of childbearing potential must have negative serum or urine pregnancy test during the current hospitalization

Exclusion Criteria

Patients fulfilling any of the following criteria are not eligible for inclusion in this study.

- BMI > 30 , or BMI < 20
- Temperature ≥ 38 C
- Systolic BP < 100 or > 180 mmHg
- Heart Rate < 50 or > 110
- Presence of a contraindication to being in proximity to a magnet (e.g. pacemaker).
- History of prior gastrostomy, gastrectomy (partial or complete), or abdominal trauma or upper-abdominal surgery.
- Patients with hematocrit $< 25\%$, or a history of blood transfusion within the 14 days prior to screening, or active life-threatening GI bleeding.
- Pregnant or nursing (lactating) women, where pregnancy is defined as the state of a female after conception and until the termination of gestation, confirmed by a positive hCG laboratory test.
- Involvement in other investigational trials within 30 days prior to screening.
- Any other medical condition(s) that may put the patient at risk or influence study results in the investigator's opinion, or that the investigator deems unsuitable for

the study. For example, large or collapsed transverse colon overlapping anterior stomach on pre-existing radiographic scan.

- Anticipated discharge < 36 hours from gastrostomy.

Method of Assigning Subjects to Treatment Groups

All patients enrolled in the study will have the PUG procedure performed. There is no prospectively enrolled comparator group.

Procedural Team

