A brief survey will be administered to the primary clinical team to assess satisfaction with the procedure and provide human factors feedback.

Subject Evaluation

Physical Exam

A physical examination will be performed by the study team at baseline, immediately following recovery from the PUG procedure and at Day 2 following PUG procedure. If

the patient remains in the hospital longer than 2 days then another physical examination will be performed at the time of discharge or on Day 30, whichever comes first.

Physical examinations will include a review of the patient's general appearance, as well as evaluation of the following body systems (see Table 2). Any abnormalities observed at baseline should be recorded on the Medical History Form of the Case Report Form (CRF). Any post-baseline new or worsening abnormalities should be recorded as an Adverse Event (AE).

Table 2 Assessments for Physical Examination

Assessment	Assessment
General appearance	Chest and lungs
Head and neck	Heart
Eyes	Abdomen
Ears	Extremities
Nose	Nervous System
Throat	Skin

Vital Signs

Pulse rate and systolic and diastolic blood pressure will be measured and recorded on the CRF at baseline, immediately prior to the PUG procedure, during the PUG procedure according to institutional norms, immediately following recovery from the PUG procedure, at Day 2 assessment and at the final assessment if the patient remains hospitalized (up to Day 30).

Clinical Laboratory Tests

Serum chemistry and hematology blood tests are performed as per usual care protocol. Results of these tests will be noted in the CRFs.

Electrocardiogram

For enrolled patients coming from an inpatient ICU, as part of usual care, a standard 12-lead ECG will be performed prior to performance of the PUG procedure. Interpretation of the tracing will be made by a member of the study team who is a qualified physician skilled in ECG interpretation. The interpretation of the 12-lead ECG will be documented by the study team member in the CRF. A copy of the ECG tracing should be labeled with the study and patient number, date, and kept in the source documents at the study site. Clinically significant abnormalities should also be recorded on the CRF as appropriate. In the event that there are significant abnormalities present on the ECG and the study

team member performing the interpretation is not the same as the proceduralist then the study team member will notify the proceduralist prior to commencing the study procedure.

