Throughout the study, the investigator must record all AEs on the AE CRF, regardless of the severity or relationship to study procedure. The investigator should treat patients with AEs appropriately and observe them at suitable intervals until the events stabilize or resolve. Adverse events may be discovered through observation or examination of the patient, questioning of the patient, complaint by the patient, or by abnormal clinical

laboratory values. In addition, AEs should also include those laboratory values that become out-of-range and are judged to be clinically significant.

Serious Adverse Event (SAE)

A *Serious Adverse Event* is any experience that suggests a significant hazard, contraindication, side effect or precaution. It is any AE that at any dose fulfills at least one of the following criteria:

- is fatal; [results in **death****; NOTE: death is an outcome, not an event]
- is Life-Threatening [NOTE: the term "Life-Threatening" refers to an event in which the patient was at immediate risk of death at the time of the event; it does not refer to an event which could hypothetically have caused a death had it been more severe]
- requires in-patient hospitalization or prolongation of existing hospitalization
- results in persistent or significant disability/incapacity
- is a congenital anomaly/birth defect
- is medically significant or requires intervention to prevent one or other of the outcomes listed above.

Important medical events that may not result in death, be life-threatening, or require hospitalization may be considered an SAE when, based upon appropriate medical judgment, that may jeopardize the patient and may require medical or surgical intervention to prevent one of the outcomes listed in this definition. A life-threatening AE is defined as an AE that placed the patient, in the view of the initial reporter, at immediate risk of death from the AE as it occurred (ie, it does not include an AE that, had it occurred in a more severe form, might have caused death).

Table 3. Adverse Events Scoring System

Pt Identifier	AE Onset	AE End	AE Code (MedRA, CTCAE)	Severity	SAE ? (Y/N)	Related-ness	Action Taken	Outcome	Comments

Severity of AE:

1 = Mild
 2 = Moderate
 3 = Severe
 4 = Life threatening or disabling

Relatedness to Intervention:

0 = Definitely unrelated
 1 = Unlikely
 2 = Possibly related
 3 = Probably related
 4 = Definitely related

Action Taken:

0 = None
1 = Dose modification
2 = Medical intervention
(specify in comments)

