language that the participant understands. Each participant must be informed that participation in the study is voluntary and that they may withdraw from the study at any time, and that withdrawal of consent will not affect their subsequent medical treatment or relationship with the treating physician. The participant or LAR should read and consider the statement before signing and dating it and should be given a copy of the signed document. No participant can enter the study before Informed consent has been obtained.

The study seeks a waiver of consent for recruitment of patients to the comparison matched historical cohort of patients who received the standard of care, PRG, procedure. The involvement in this arm of the research study presents no more than minimal risk of harm to participants and involves no procedures for which written consent is normally required outside of the research context. The same data will be collected in a retrospective fashion using electronic medical record and medical center data sources. Per the study protocol outlined elsewhere, no identifiable patient information will be collected to ensure confidentiality.

Protocol Adherence

Investigators ascertain they will apply due diligence to avoid protocol deviations. This protocol defines the study objectives, the study procedures and the data to be collected on study participants. Under no circumstances should an investigator collect additional data or conduct any additional procedures for any research related purpose involving any investigational drugs or devices.

Protocol Amendments

Alterations to the protocol can only be made in a written protocol amendment that must be approved by the PI, CoapTech, and the REB. Only amendments that are required for imminent threat to patient safety may be implemented prior to REB approval. Notwithstanding the need for approval of formal protocol amendments, the investigator is expected to take any immediate action required for the safety of any patient included in this study, even if this action represents a deviation from the protocol. In such cases, CoapTech should be notified of this action and the REB at the study site should be informed within 10 working days or less, if required by local regulations.

Data Handling and Record Keeping

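### Complications are ascertained differently in the PUG and PRG cohorts, which can bias their comparison in a direction the documents do not settle

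*Protocol*

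**What the plan says.** The Synopsis (Secondary Objectives, item 1) introduces the comparison with a retrospective matched PRG cohort as follows: "While acknowledging that the study is underpowered, to perform a preliminary direct comparison". Item 1a is a composite of accidental puncture of listed organs or vessels, injury needing surgical repair, and post-procedure infection. Item 1b lists SAEs by category and ends with an open category, Other.

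For PUG, Physical Exam schedules study-team examinations at baseline, "immediately following recovery from the PUG procedure and at Day 2 following PUG procedure", and again at discharge or Day 30 for patients still in hospital. It adds: "Any post-baseline new or worsening abnormalities should be recorded as an Adverse Event (AE". The Adverse Event section states: "Throughout the study, the investigator must record all AEs on the AE CRF, regardless of the severity or relationship to study procedure". It names examination and questioning of the patient among the ways events may be found.

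For PRG, Method of Assigning Subjects to Treatment Groups states: "There is no prospectively enrolled comparator group". Informed Consent, and again the consent section for the retrospective cohort, describes the source: "The same data will be collected in a retrospective fashion using electronic medical record and medical center data sources".

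Operator opinion enters the composite at one point, the vessel item: "larger blood vessels (that require operative repair or result in significant blood loss in the opinion of the operator".

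Data Analysis in the Synopsis plans descriptive statistics for the comparison. The SAP says only that the study is not powered to show a difference from radiologic placement.

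**The concern.** A comparison of event rates is interpretable only if an event has a similar chance of being found and counted in each group. Here one group is examined on a schedule by a team that must record every new abnormality, and the other is represented by whatever was charted in routine care. The Protocol gives no abstraction form, chart-level event definitions, PRG time window or adjudication process to bring the two together.

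The acknowledgement of low power concerns imprecision, not unequal measurement, and a larger control cohort would not remove the difference. The SAP says further powered studies will be warranted if this one succeeds, so a PUG-PRG contrast may be read as early evidence even though it is descriptive.

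**Working it through.** **The plan's own figures.** The SAP's quantified statements for n = 25 are single-arm. The chance of at least one event at a 6.3% rate is 1 − (1 − 0.063)^25 = 80.3%, against 80% stated. With no events, the two-sided 95% upper bound is 1 − 0.025^(1/25) = 13.7%, as stated. Neither bears on the PUG-PRG comparison, for which the plan gives no figure.

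**Where the sources differ, item by item.**
- *Surgical repair, salvage surgery, sepsis, peritonitis, recognised organ puncture:* normally charted in either cohort, so the capture gap is probably small.
- *Infection in item 1a:* no severity threshold is given. A mild infection found at the Day 2 study examination could count for PUG, while its PRG equivalent was never charted.
- *SAEs classed as Other in item 1b:* the SAE definition admits events by medical judgement, which was exercised prospectively for PUG and must be reconstructed for PRG.
- *Larger vessels:* operator opinion on blood loss is an alternative to operative repair. For past PRG cases it may not be recoverable.

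**Illustration.** Inputs: true rate p = 4% in both groups (the SAP's approximate standard-of-care rate); 25 PUG subjects (SAP). Assumptions not in the documents: 25 PRG controls, and the capture probabilities. Observed rate = p × capture; expected events = 25 × p × capture. The last two columns treat the counts as independent binomials.

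| PUG capture | PRG capture | Expected events, PUG vs PRG | Gap, PUG − PRG (points) | P(PUG count higher) | P(PRG count higher) |
|---|---|---|---|---|---|
| 100% | 100% | 1.0 vs 1.0 | 0 | 34.5% | 34.5% |
| 100% | 90% | 1.0 vs 0.9 | +0.4 | 36.8% | 31.3% |
| 100% | 75% | 1.0 vs 0.75 | +1.0 | 40.5% | 26.4% |
| 100% | 50% | 1.0 vs 0.5 | +2.0 | 47.3% | 17.9% |
| 90% | 100% | 0.9 vs 1.0 | −0.4 | 31.3% | 36.8% |
| 75% | 100% | 0.75 vs 1.0 | −1.0 | 26.4% | 40.5% |
| 50% | 100% | 0.5 vs 1.0 | −2.0 | 17.9% | 47.3% |

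Example: at 50% chart capture the observed PRG rate is 4% × 0.5 = 2%, the gap is 4% − 2% = 2 points, and 25 × 0.02 = 0.5 events are expected. At a 3% true rate, the higher rate in the Protocol's Rationale of Study Design, the gaps are 0.3, 0.75 and 1.5 points in either direction.

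**The case against.** A reader might infer that PUG will show more complications than PRG. The documents do not support so firm a direction. The study is unblinded and the operator belongs to the study team, so judgement can lower PUG counts as well as raise them. The matching variables are not stated, and PUG subjects pass BMI, vital-sign and anatomical restrictions, so imbalance could also act either way.

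A reader might also give operator opinion more weight than it has: it qualifies one item of the composite. Similarly, the rule that every new abnormality is an AE feeds general AE reporting, and most such findings never enter the composite. The sources also overlap, since Data Handling and Record Keeping draws PUG data partly from the medical file.

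Finally, the comparison is labelled preliminary and underpowered, is descriptive, and feeds no decision rule. The primary safety outcome is single-arm and does not use the PRG cohort.

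These arguments limit the direction, size and consequence of the problem. They do not show that capture is equal. An unknown direction leaves the contrast hard to read whichever way it falls, and the stated caveat does not cover unequal measurement.

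**Conclusion.** The point stands as a recommended change. Ascertainment differs between the cohorts, nothing in the plan harmonises it, and the descriptive comparison can be biased when true rates are equal. An excess of PUG events is plausible, chiefly through non-severe infection and the Other category, but net direction and size cannot be determined from the documents.

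The 0.4-2.0 point gap at a 4% rate rests on assumed chart capture of 50-90% and full PUG capture; it is an illustration, not an estimate. Expressing it as a ratio (1/0.9 = 1.1 to 1/0.5 = 2.0) would only restate the assumed capture and would hide that the shift is 0.1-0.5 expected events in 25. Chance dominates at that scale. The primary single-arm safety analysis is unaffected.

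**What to change.** For the PUG-PRG comparison only:

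- Abstract both cohorts from routine records with one form and the same 48-hour window, the period the Protocol's Key Secondary Objectives already give for serious complications.
- Count components that records can verify: documented organ puncture, operative repair, documented treated infection, and significant blood loss documented in the record.
- Do not count PUG findings known only from study-specific examinations. This must be explicit, because PUG examination results may be filed in the medical record and would otherwise re-enter through abstraction.

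Keep the prospective AE data and the a priori definition for the primary single-arm safety analysis. Report the PUG rate both ways, label the record-based version as a departure from the a priori definition, and state the remaining ascertainment difference as a limitation.

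Cost: up to 25 extra chart abstractions and an amendment to the Protocol and SAP; SAP wording alone may not suffice, because Protocol Adherence bars data collection beyond the protocol. There will also be a second PUG rate that may differ from the primary one and needs explaining.

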A single-center, feasibility study to evaluate the use and safety of the Percutaneous
Ultrasound Gastrostomy technique

Principal Investigator:

[name] FRCPC
Division Head for Interventional Radiology
London Health Sciences Centre

NCT03575754

Statistical Analysis Plan

The primary objective of the proposed study is thus the demonstration of safety and feasibility of a novel gastrostomy tube placement (PUG) method using the PUMA-G device in this first-in-human pilot study (n=25). A sample size of 25 was chosen for this study because it provides 80% chance of seeing at least one serious-device related event assuming the event rate is at least 6.3% and a 90% chance of seeing at least one event if the true event rate is at least 11.3%. If no events are observed, then the 95% two-sided upper bound exact binomial CI for the event rate is 13.7%. Hence, the planned sample size has both power to detect at least one event should the event rate be consistent with literature estimates and is sufficient to obtain an upper bound on the event rate of less than 15%; so the planned sample size is considered adequate for this feasibility study. See Table 1 below for calculations.

Table 1: Sample size calculations to optimize ability to detect PUG adverse event

Sample Size	Provides 80% to detect at least one study adverse event if the actual adverse event rate is:	Provides 90% to detect at least one study adverse event if the actual adverse event rate is:	95% One-sided Upper bound for Safety Event Rate	95% Two-sided Upper bound for Safety Event Rate
25	6.3%	8.8%	11.3%	13.7%

It is acknowledged that as a feasibility study, the proposed clinical evaluation is not powered to demonstrate a difference in adverse event outcomes when compared to the standard of care, radiologic gastrostomy tube placement method. In part, this is due to the relatively low rate of complications placement (~4% complication rate). Sample sizes numbering in the thousands would be necessary. These infeasible sample sizes at this stage highlight the need to initially evaluate the PUMA-G device in a feasibility study, per standard development of most medical devices. If successful, further powered studies will be warranted.

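### The SAP text gives 11.3% as the event rate for a 90% chance of seeing an event with 25 subjects; its own Table 1 and the arithmetic give 8.8%

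*SAP*

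**What the plan says.** The SAP's sample-size paragraph supports n = 25 with three properties.

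- **80% detection.** The threshold rate for an 80% chance of at least one serious device-related event is put at 6.3%.
- **90% detection.** "a 90% chance of seeing at least one event if the true event rate is at least 11.3" (per cent).
- **Bound with zero events.** "If no events are observed, then the 95% two-sided upper bound exact binomial CI for the event rate is 13.7" (per cent).

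The paragraph then points to SAP Table 1 for the calculations. The table has one row, n = 25. Under the heading "Provides 90% to detect at least one study adverse event if the actual adverse event rate is" the value is 8.8%. Under the next heading, "95% One-sided Upper bound for Safety Event Rate", it is 11.3%. The 80% column (6.3%) and the two-sided bound column (13.7%) agree with the text.

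**The concern.** The text and the table it cites give different values for one quantity, the true event rate at which 25 subjects have a 90% chance of showing at least one event. The value in the text is the table's entry for something else. A detection threshold describes the chance of seeing an event before the data are in. An upper bound describes which rates remain compatible with the data once no events have been seen.

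The protocol's primary outcome is the number and severity of device-related adverse events, and the SAP paragraph is where an ethics board, safety board or regulator would look to learn what event rate the study can be expected to reveal. A reader who relies on the text takes away the wrong design property. A reader who checks the table finds that the SAP disagrees with itself.

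**Working it through.** **Inputs, all from the SAP:** n = 25, single arm; text figures 6.3% (80%), 11.3% (90%) and 13.7% (two-sided bound); Table 1 row 6.3%, 8.8%, 11.3%, 13.7%.

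**Formulas.** With true event rate p, the chance of at least one event in 25 subjects is 1 − (1 − p)^25. The rate that gives a chance of c is p = 1 − (1 − c)^(1/25). With 0 events in 25, the exact binomial upper bound is 1 − 0.05^(1/25) (one-sided 95%) or 1 − 0.025^(1/25) (two-sided 95%).

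**Figures in the text that reproduce**

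- 80% detection: 1 − 0.20^(1/25) = 6.23%. At the stated 6.3% the chance is 1 − 0.937^25 = 80.3%.
- Two-sided bound: 1 − 0.025^(1/25) = 13.72%, stated as 13.7%.

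**The figure in question**

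| Quantity at n = 25 | Calculation | Result | SAP text | SAP Table 1 |
|---|---|---|---|---|
| Rate for a 90% chance of at least one event | 1 − 0.10^(1/25) | 8.80% | 11.3% | 8.8% |
| One-sided 95% upper bound, 0/25 events | 1 − 0.05^(1/25) | 11.29% | not given | 11.3% |
| Chance of at least one event at 8.8% | 1 − 0.912^25 | 90.0% | – | 90% |
| Chance of at least one event at 11.3% | 1 − 0.887^25 | 95.0% | 90% | – |

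All four event-rate figures in the table reproduce under their own headings. In the text, only the 90% figure fails.

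**Could another method give 11.3% for 90%?** A Poisson approximation gives −ln(0.10)/25 = 9.2%. Keeping 11.3% and solving for the sample size gives ln(0.10)/ln(0.887) = 19.2, so 11.3% would be the 90% threshold at about 19 subjects, not 25. Neither explains the text.

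**Size of the discrepancy.** 11.3 − 8.8 = 2.5 percentage points; 2.5/8.8 = 28% of the correct threshold.

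**The case against.** The strongest reply is that the sentence is literally true and nothing depends on it. It says at least 11.3%, and at any such rate the chance is 95% or more, which exceeds 90%. The error understates what the design can detect, so it does not inflate the case for 25 subjects. No analysis or decision threshold in either document uses the figure. The closing claim of an upper bound below 15% rests on 13.7%, which is right. The correct 8.8% is already in the table below.

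Most of this stands, and it limits the practical consequence. The literal reading does not rescue the sentence, however. The parallel statement for 80% uses 6.3%, which is the actual threshold, and the table presents both rates as thresholds. Read in the same way, 11.3% is wrong for 90%.

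Two further points are fair. First, how the slip arose is an inference. A value taken from the adjacent column is the likely cause, but 11.3% is also the rate that gives a 95% chance of an event, so 90% could have been written for 95%. The table has a 90% column and no 95% detection column, which favours correcting the rate. Second, correcting the figure does not settle whether 25 subjects are enough. At the roughly 4% complication rate that the SAP quotes for radiologic placement, the chance of seeing an event is 1 − 0.96^25 = 64%, whichever figure the sentence carries. That is a separate question.

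**Conclusion.** The concern holds. The 90% detection threshold for 25 subjects is 8.8%, as SAP Table 1 shows; the 11.3% in the text is the one-sided 95% upper bound for zero events. The text overstates the threshold by 2.5 percentage points (28% relative), and the chance it describes as 90% is in fact 95.0%.

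The result assumes only independent subjects with a common event rate, the binomial model that reproduces every other figure in the paragraph and table. The error is conservative and leaves n = 25, the 6.3% and 13.7% figures and the below-15% conclusion intact. It should be corrected because it is a demonstrable numerical error in one of the two detection statements that justify the sample size.

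**What to change.** In the SAP sample-size paragraph, replace 11.3% with 8.8% in the statement about a 90% chance, so that text and table agree. If 11.3% is to appear in the text, give it in a separate sentence as the one-sided 95% upper bound on the event rate when 0 of 25 subjects have an event, next to the two-sided 13.7%. Table 1 needs no change.

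The cost is one figure in the text. The sample size, analyses and trial conduct are unaffected.
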